8 EXPLORATORY ENDPOINTS

Several measures of efficacy in reducing respiratory morbidity in the short and long term will be explored. The trends and effects observed in this study will be used to determine appropriate efficacy outcome variables and the numbers of infants that would be required to be enrolled in a larger Phase 2 or Phase 3 study.

8.1 Primary Endpoint: Long Term Efficacy – 12 months

The primary outcome of the study will be survival without CRM through 12 months CGA as measured by a validated respiratory diary based scoring system (presence of wheezing and/or coughing 2 days per week for 3 consecutive weeks) and pulmonary questionnaires (decrease in respiratory illness requiring medications, unscheduled medical visits and/or ER or hospital admissions) which have been shown to correlate closely with abnormalities on pulmonary function testing. The 12 month CGA endpoint has been shown to be more predictive of respiratory morbidity at two years of life than a diagnosis of BPD at 36 weeks CGA in previous studies of high frequency oscillatory ventilation in preterm infants.

8.2 Secondary Endpoints: Long Term Efficacy – 6 & 18 months

A secondary outcome of the study will be survival without CRM through 6 months CGA as measured by validated respiratory diaries (presence of wheezing and/or coughing 2 days per week for 3 consecutive weeks) and pulmonary questionnaires (decrease in respiratory illness requiring medications and/or hospitalization) which have been shown to correlate closely with abnormalities on pulmonary function testing. Infants will be also be evaluated by physical examinations at 18 months CGA to evaluate respiratory status, growth, and neurological development.

8.3 Secondary Endpoints: Short Term Efficacy

Short term efficacy evaluations will include time of mechanical ventilation, oxygen requirement at 36 weeks CGA, and survival without BPD at 36 weeks CGA (or NICU discharge) as measured by oxygen challenge testing. Oxygen challenge testing involves the withdrawal of supplemental oxygen for a 30 minute period, during which the infant is closely monitored. At the end of the 30' period, oxygenation as

measured by pulse oximetry is recorded and the infant is placed back on supplemental oxygen. The infant's BPD status is then determined by oxygen saturation; a diagnosis of BPD will be made if the infant's oxygen saturation is 90% or less ($\leq 90\%$) at or before the end of the thirty minute period. If the infant's oxygen level remains above 90% for the entire period, then the diagnosis will be "No BPD". Failure to complete the test due to respiratory distress would be scored as severe BPD. The severity of BPD will be assessed using NIH consensus guidelines for infants born at <32 weeks PMA based on oxygen requirements at 28 days post-natal age and at 36 weeks PMA or at NICU discharge (whichever comes first), as described in Jobe and Bancalari. (2001), as follows:

NIH criteria for assessing severity of BPD

| | |
|---|---|
| Gestational age at birth | < 32 weeks PMA |
| Time point of assessment | 36 weeks PMA or DC home, whichever comes first |
| Treatment with oxygen > 28 days plus | |
| Mild BPD | Breathing room air at 36 weeks PMA or DC, whichever comes first |
| Moderate BPD | Need* for <30% oxygen at 36 weeks PMA or DC, whichever comes first |
| Severe BPD | Need* for $\geq 30\%$ oxygen and/or positive pressure (PPV or NCPAP) at 36 weeks PMA or DC, whichever comes first |

Definition of abbreviations: BPD = bronchopulmonary dysplasia; NCPAP = nasal continuous positive airway pressure; PMA = postmenstrual age; PPV = positive-pressure ventilation; DC = discharge.

* Physiologic need for oxygen is determined by oximetry during oxygen withdrawal challenge.

Taken from Jobe AH, Bancalari E. Bronchopulmonary Dysplasia. Am J Resp Crit Care Med 2001;163:1723

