6.4 Subsequent Examinations

During the initial 4-week, post-dosing period (28 days), serum, urine, stool, and TAF samples will be taken on days 1 (baseline) and 28. If possible, samples will also be collected on days 7, 14, and

21 only if scavenged blood from clinical specimens is available. Serum and urine samples for CC10 analysis will also be collected on visit 20 (see table 3). TAF samples on day 28 will only be collected if the infant is still intubated.

A schedule of clinical and pharmacological evaluations is shown in Table 2. During the initial active-treatment period, formal study visits and procedures will be performed on a weekly basis. Weekly formal study visits will review concomitant medications, adverse experiences, collection of vital signs, growth parameters (weight, length, head circumference), physical and neurologic examinations, respiratory status (days of mechanical ventilation, days of nasal CPAP, oxygen requirements), nutritional support data and safety laboratories (electrolytes, glucose, calcium, hepatic and renal function, complete blood count with differential). Maternal history including smoking, atopy, and asthma will also be collected. In order to document that initial severity of illness is comparable between groups, a Score for Neonatal Acute Physiology Version II (SNAPPE-II) will be recorded during the initial visit. Cranial sonography to detect intraventricular hemorrhage (IVH) will be performed within 7 ± 2 days of enrollment and to detect periventricular leukomalacia (PVL) within 28 ± 2 days per standard of care for infants of this gestational age.

TABLE 2: SCHEDULE OF EVALUATIONS
(**BOLDED** text Represent Study-Related Procedures)

| Evaluation | Visit 1 | Visit 2 | Visit 3 | Visit 4 | Visit 5 |
|--|--------------------|---------|---------|---------|---------|
| Study day | day 1 ⁵ | day 7 | day 14 | day 21 | day 28 |
| Inclusion/exclusion criteria | X | | | | |
| Informed consent | X | | | | |
| Study drug administration | X | | | | |
| Head ultrasound ² | | X | | | |
| Chest X-ray ² | X | | | | |
| Physical examination/Vital Signs/Anthropomorphics including eye exam | X | X | X | X | X |
| Respiratory and Nutritional Data/ Concomitant Meds | X | X | X | X | X |
| Adverse events | X | X | X | X | X |
| Safety laboratories⁴ (Mandatory study-related) | X | | | | X |
| Study samples⁴ | | | | | |
| Mandatory blood samples (anti-CC10 titer) | X | | | | X |
| Scavenged blood (CC10 tests¹) | | X | X | X | |

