Power Analysis: A total of 88 preterm infants will be randomized to placebo, lower dose, or higher dose rhCC10 with an allocation ratio of 2:1:1. The primary analysis will be the comparison of placebo versus both rhCC10 dose groups combined. The prior trial demonstrated that the two doses are likely to yield similar results. Two doses will be used for the purpose of extending the safety profile for each individual dose, as that safety data may facilitate the choice of dose for a future Phase III confirmatory study. For SAEs or AEs with background rates of 5%, 10%, or 15%, the sample size of 22 in either dosing group will provide a probability of observing it of 68%, 90%, and 97%, respectively. The proposed trial is powered for the comparison of the two doses combined versus placebo for the composite endpoint of death or development of CRM. Secondarily, the study will yield effect size estimates for each individual dose versus placebo. Our assumptions regarding the comparison of placebo versus rhCC10 are based on the previous study with 7 placebo, 8 lower dose, and 7 higher dose infants (one infant in each of the rhCC10 treatment groups died). It is important to address the combined endpoint of death or re-admission to the hospital for respiratory problems. In the previous study, one loss-to-follow-up occurred in each of the three experimental groups and one death occurred in each of the rhCC10 groups. At 6 months, 3 of the 6 infants on placebo with follow-up were re-admitted to the hospital for respiratory problems and none of the 11 subjects treated with either rhCC10 dose with follow-up data were re-hospitalized. A realistic and conservative assumption for the 3 lost-to-follow-up babies is that they all either died or had respiratory disease. Then the proportions with disease or death on placebo and rhCC10 are assumed to have been 0.57 and 0.27. If the proportions in the proposed study are similar, with 44 subjects on placebo and 44 subjects in the two dose groups combined, power will be 82% with $\alpha=0.05$. nQuery Advisor version 6 was used.

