Data will be summarized for the total cases and by treatment group with respect to: 1) baseline demographic and clinical characteristics and 2) efficacy and safety observations and measurements. Analyses will be conducted on both the intention-to-treat (ITT) and 'per protocol' cases. Between-treatment or between-group comparisons will be examined using chi-square tests (or Fisher's Exact tests when cell frequencies are small) for categorical outcomes and Student t-tests (alternatively, Wilcoxon Rank Sum Test) for scalar measures. Two-sided statistical tests will be conducted and the significance level will be set at 0.05 for each primary test. The efficacy and safety analyses will be conducted on both the ITT and per protocol population. ITT cases will be all randomized subjects who receive the study medication, while per protocol cases will be randomized subjects who complete the study (including all cause deaths) without any major deviations from the protocol procedures. Descriptive statistics will be used to detail the sample characteristics. Between-treatment arm

differences on key baseline demographic and clinical characteristics will be tested. This latter step will be used to identify potential pre-treatment covariates for subsequent secondary analyses. Key baseline variables include race, gender, length, weight, head circumference, SNAPPE-II score, and gestational age. Descriptive statistics for the total exposure to study drug during the treatment period (number of doses), timing of initial study dose, timing of discontinuation in the event of early termination, and rate of study dropout will be provided. Between-treatment differences will be tested using the statistical methods described earlier. Concomitant medications will be summarized by therapeutic/pharmacological class and treatment group. In addition, they will be listed by treatment group, name of drug, dates administered, dose, frequency and indication.

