Efficacy evaluation: If CC10 is more efficacious than placebo, the CC10 treatment groups will have a higher rate of survival without BPD at 36 weeks CGA and/or survival without CRM at 12 months CGA (we are exploring which of these factors are more accurate predictors of long term respiratory morbidity). A 2 x 2 chi square test will be conducted to examine treatment differences in this binary endpoint and Kaplan-Meier survival curves will be constructed and any differences between the treatments will be tested using a Cox Proportional Hazards Regression Model. Secondly, a logistic regression will be employed to further detail the main and interaction effects of treatment and centers on the primary outcome. Odds Ratios (OR) with 95% confidence intervals (CI) will be provided. Subjects who die from respiratory causes before 12 months CGA will be considered treatment failures in both the ITT and per protocol analyses, and the last observation carried forward (LOCF) imputation method will be applied for early dropouts. For those subjects without diary data at any time point, respiratory status will be estimated based on available data during the follow-up period, including O₂ challenge test, pulmonary questionnaires, and use of asthma medications.

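### Days of mechanical ventilation are compared with no rule for death, so an arm with more early deaths can appear to have shorter ventilation

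*Combined protocol and SAP*

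**What the plan says.** Section 8.3 introduces the short-term secondary endpoints with "Short term efficacy evaluations will include time of mechanical ventilation". It gives no time window and does not say how an infant who dies is counted. BPD, in the same sentence, is framed as survival without BPD, so death is built into that outcome.

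Section 6.4 lists what the weekly visits review, including "respiratory status (days of mechanical ventilation, days of nasal CPAP, oxygen requirements". Ventilation is therefore available as a number of days.

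Section 8.5 gives the general test rule: "Student t-tests (alternatively, Wilcoxon Rank Sum Test) for scalar measures". It also defines the analysis sets. For the first, "ITT cases will be all randomized subjects who receive the study medication". The per-protocol set expressly keeps deaths from any cause. Infants who die are thus in both sets.

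The efficacy paragraph of section 8.5 has three provisions that might bear on death:
- "Subjects who die from respiratory causes before 12 months CGA will be considered treatment failures in both the ITT and per protocol analyses"
- "the last observation carried forward (LOCF) imputation method will be applied for early dropouts"
- "Kaplan-Meier survival curves will be constructed and any differences between the treatments will be tested using a Cox Proportional Hazards Regression Model"

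All three stand in a paragraph about survival without BPD and survival without CRM. Ventilation time is not mentioned there.

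**The concern.** Ventilation ends either at extubation or at death, and a plain count of days does not separate the two. An infant who dies on the ventilator on day 3 contributes 3 days. A survivor extubated on day 10 contributes 10. On a scale where fewer days is better, the death ranks ahead of the survivor.

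If early deaths are balanced, this adds noise but no bias. If one arm has more of them, that arm's ventilation looks shorter even when the drug has no effect on ventilation.

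The measure has a use beyond this trial. The opening of section 8 says that the trends seen here will guide the choice of outcome variables and the sample size of a larger study. An apparent gain produced by deaths could carry over into that design.

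**Working it through.** **Does any rule already cover it?**

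| Provision in section 8.5 | Why it does not settle ventilation days |
|---|---|
| Respiratory deaths are treatment failures | Covers respiratory causes only; a failure has no value on a scale of days |
| LOCF for early dropouts | Deaths are not named; carrying the last count forward would leave the short count in place |
| Kaplan-Meier and Cox | Attached to the binary survival endpoint |

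None does.

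**The plan's own figure.** The documents give no figure for ventilation time. The only power statement is for the primary endpoint: 0.57 v 0.27, 44 v 44, two-sided 0.05, stated as 82%. With pooled variance, z = [0.30 × √44 − 1.96 × √(2 × 0.42 × 0.58)] / √(0.57 × 0.43 + 0.27 × 0.73) = 0.935, which is a power of 82.5%. It reproduces, and nothing below changes it.

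**Inputs for the size**
- From section 8.5: 44 placebo v 44 rhCC10 with doses pooled, two-sided 0.05, t-test or Wilcoxon.
- From section 2.5.1: pilot deaths of 2/15 = 13.3% on rhCC10 and 0/7 on placebo, used only as an illustrative contrast.
- Assumed, because the documents give no ventilation data: lognormal duration, median 14 days, log SD 0.9, the same in both arms. Deaths are independent of ventilation need. Days stop at extubation or death, whichever comes first.

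**Hand check of the bias in the mean.** Mean duration is 14 × exp(0.9²/2) = 21.0 days. A death uniform on days 1-10 falls at 5.5 days on average, so such an infant counts at most about 5.5 days. The arm mean is then shortened by about 0.133 × (21.0 − 5.5) = 2.1 days.

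**Simulation** (3,000 to 4,000 trials per row; a trial counts if p < 0.05 in favour of rhCC10; nominal 2.5%):

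| Deaths, placebo v rhCC10 | Timing | Mean difference | t-test | Wilcoxon |
|---|---|---|---|---|
| 0 v 13.3% | all days 1-10 | −2.1 days | about 7% | about 12% |
| 0 v 13.3% | half days 1-10, half days 21-42 | −1.3 days | about 5% | about 6% |
| 0 v 13.3% | all days 21-42 | −0.6 days | about 3% | about 3% |
| 10% v 15% | all days 1-10 | −0.8 days | about 3% | 4-5% |
| 10% v 10% | all days 1-10 | about 0 | about 2% | about 2.5% |

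Repeat runs differ by a point or so in the first row and by less elsewhere.

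**Other durations.** With log SD 1.0, a cap at 84 days, deaths on days 1-7 and medians from 7 to 28 days, the Wilcoxon rate for 0 v 2/15 is 8.0-16.2%, and for 5% v 15% it is 7.0-11.2%. The direction is the same and the size moves with the assumptions.

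**After the change.** With ventilator-free days to day 28 and death by day 28 ranked worst, the Wilcoxon false-benefit rate for 0 v 13.3% early deaths falls to about 0.1%. With 10% deaths in each arm it stays at about 2.5%.

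**The case against.** The strongest reply is that the plan leaves the endpoint undefined and does not wrongly define it. Section 8.3 names no test, and the t-test or Wilcoxon link comes from the general rule for scalar measures. The analyst might sensibly use survivors only or time to extubation. That is a fair reading, but the general rule, the recorded variable and the analysis sets together lead to the plain count, and nothing in the plan directs the analyst elsewhere.

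Several stronger readings are tempting, and the documents do not support them.

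- **That the pilot shows excess mortality on rhCC10.** A reader might infer this from "one infant in each of the rhCC10 treatment groups died", with none on placebo. But 2/15 v 0/7 gives Fisher p = 1.0. If two deaths fall at random among 22 infants, both are on rhCC10 with probability C(15,2)/C(22,2) = 105/231 = 45%. Section 2.5.1 says neither death was judged attributable to the drug.
- **That 7-12% is the rate to expect in this trial.** That figure needs every death to be early. One pilot death followed NEC, and section 2.6 places NEC in that trial 3-6 weeks after dosing. The other death has no stated date.
- **That mortality would be hidden.** Death is part of the primary composite and of survival without BPD, and it is an SAE reported to the DSMB. A reader would see the deaths beside any shorter ventilation.
- **That being listed first gives the measure rank.** The plan states no ordering, and section 8 is headed as exploratory.
- **That oxygen requirement at 36 weeks has the same defect.** It does not score a death as a good value. It is simply not observed in infants who have died, and survival without BPD is its death-inclusive counterpart at the same time point.

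These points limit the size and the consequence. They do not supply a rule for death.

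**Conclusion.** The point holds in this form: ventilation days are compared by a plain two-sample test in sets that include deaths, no rule says how death counts, and an early death on the ventilator therefore enters as a favourable value.

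The bias requires deaths that are both unequal between arms and early relative to usual ventilation time. Under the stated assumptions, false benefit runs from about 7% (t-test) and 12% (Wilcoxon) when all deaths are early to about 3%, close to nominal, when all fall on days 21-42. With equal mortality there is none. Duration, death rates and death timing are assumptions, so the figures show direction and rough size only.

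This concerns a secondary endpoint in an exploratory phase 2 trial. The primary analysis, its power and the sample size are unaffected. It is a cheap improvement, worth making because the plan intends to use such measures in designing the next study.

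**What to change.** Before unblinding, amend sections 8.3 and 8.5 as follows:

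1. Define the measure as ventilator-free days through day 28. Death from any cause by day 28 is ranked worst, below zero ventilator-free days. Compare by Wilcoxon.
2. State how days after re-intubation, and days missing after withdrawal, are counted.
3. Report deaths by arm next to the result, and report ventilation days in survivors descriptively, without a test.
4. State that oxygen requirement at 36 weeks is observed only in survivors and is to be read together with survival without BPD.

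The cost is analysis wording. The documents describe days of ventilation reviewed at weekly visits up to day 28, not a daily status record; those counts and the deaths are enough. No visit, sample or infant is added.

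There are two downsides. The measure becomes a composite of survival and ventilation, so a difference has to be read with its components. It also ignores ventilation after day 28: under the assumed distribution about 22% of infants would need longer (P(Z > ln 2 / 0.9) = P(Z > 0.77) = 0.22). Time to extubation alive, with death as a competing event, is a reasonable alternative if later ventilation matters to the sponsor.

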8.4 Secondary Endpoints: Safety and Efficacy - Adverse Events

The safety of the study drug will continue to be assessed by comparing the incidence of adverse events and serious adverse events in the treatment and placebo groups to each other and to the historical incidence of the adverse events at each institution. Safety evaluations will include all serious adverse events up to at least 12 months CGA, and routine laboratory monitoring prior to NICU discharge (CBC, electrolytes, liver function studies, urinalysis, head ultrasound). In addition to evaluating the safety of rhCC10, preliminary efficacy of rhCC10 in this patient population may also be indicated by decreases in the numbers of all SAEs and/or specific types of SAEs (ie. IVH, PVL, ROP, sepsis, infection, etc.).

8.5 Statistical Considerations.

Power Analysis: A total of 88 preterm infants will be randomized to placebo, lower dose, or higher dose rhCC10 with an allocation ratio of 2:1:1. The primary analysis will be the comparison of placebo versus both rhCC10 dose groups combined. The prior trial demonstrated that the two doses are likely to yield similar results. Two doses will be used for the purpose of extending the safety profile for each individual dose, as that safety data may facilitate the choice of dose for a future Phase III confirmatory study. For SAEs or AEs with background rates of 5%, 10%, or 15%, the sample size of 22 in either dosing group will provide a probability of observing it of 68%, 90%, and 97%, respectively. The proposed trial is powered for the comparison of the two doses combined versus placebo for the composite endpoint of death or development of CRM. Secondarily, the study will yield effect size estimates for each individual dose versus placebo. Our assumptions regarding the comparison of placebo versus rhCC10 are based on the previous study with 7 placebo, 8 lower dose, and 7 higher dose infants (one infant in each of the rhCC10 treatment groups died). It is important to address the combined endpoint of death or re-admission to the hospital for respiratory problems. In the previous study, one loss-to-follow-up occurred in each of the three experimental groups and one death occurred in each of the rhCC10 groups. At 6 months, 3 of the 6 infants on placebo with follow-up were re-admitted to the hospital for respiratory problems and none of the 11 subjects treated with either rhCC10 dose with follow-up data were re-hospitalized. A realistic and conservative assumption for the 3 lost-to-follow-up babies is that they all either died or had respiratory disease. Then the proportions with disease or death on placebo and rhCC10 are assumed to have been 0.57 and 0.27. If the proportions in the proposed study are similar, with 44 subjects on placebo and 44 subjects in the two dose groups combined, power will be 82% with $\alpha=0.05$. nQuery Advisor version 6 was used.

Data will be summarized for the total cases and by treatment group with respect to: 1) baseline demographic and clinical characteristics and 2) efficacy and safety observations and measurements. Analyses will be conducted on both the intention-to-treat (ITT) and 'per protocol' cases. Between-treatment or between-group comparisons will be examined using chi-square tests (or Fisher's Exact tests when cell frequencies are small) for categorical outcomes and Student t-tests (alternatively, Wilcoxon Rank Sum Test) for scalar measures. Two-sided statistical tests will be conducted and the significance level will be set at 0.05 for each primary test. The efficacy and safety analyses will be conducted on both the ITT and per protocol population. ITT cases will be all randomized subjects who receive the study medication, while per protocol cases will be randomized subjects who complete the study (including all cause deaths) without any major deviations from the protocol procedures. Descriptive statistics will be used to detail the sample characteristics. Between-treatment arm

differences on key baseline demographic and clinical characteristics will be tested. This latter step will be used to identify potential pre-treatment covariates for subsequent secondary analyses. Key baseline variables include race, gender, length, weight, head circumference, SNAPPE-II score, and gestational age. Descriptive statistics for the total exposure to study drug during the treatment period (number of doses), timing of initial study dose, timing of discontinuation in the event of early termination, and rate of study dropout will be provided. Between-treatment differences will be tested using the statistical methods described earlier. Concomitant medications will be summarized by therapeutic/pharmacological class and treatment group. In addition, they will be listed by treatment group, name of drug, dates administered, dose, frequency and indication.

Efficacy evaluation: If CC10 is more efficacious than placebo, the CC10 treatment groups will have a higher rate of survival without BPD at 36 weeks CGA and/or survival without CRM at 12 months CGA (we are exploring which of these factors are more accurate predictors of long term respiratory morbidity). A 2 x 2 chi square test will be conducted to examine treatment differences in this binary endpoint and Kaplan-Meier survival curves will be constructed and any differences between the treatments will be tested using a Cox Proportional Hazards Regression Model. Secondly, a logistic regression will be employed to further detail the main and interaction effects of treatment and centers on the primary outcome. Odds Ratios (OR) with 95% confidence intervals (CI) will be provided. Subjects who die from respiratory causes before 12 months CGA will be considered treatment failures in both the ITT and per protocol analyses, and the last observation carried forward (LOCF) imputation method will be applied for early dropouts. For those subjects without diary data at any time point, respiratory status will be estimated based on available data during the follow-up period, including O₂ challenge test, pulmonary questionnaires, and use of asthma medications.

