will be telephone visits by the study coordinator. Visit 13 (5 months CGA) will include explanation of the 6 month 28-day respiratory symptom and quantitative diaries which will be recorded daily (from 5-6 months CGA) for a 4 week period by filling a hard copy of the 28-day diaries. Visit 14 (6 months CGA \pm 2 weeks) will include Visit 6 parameters, review of the 28-day diaries (presence of persistent coughing, wheezing, or use of respiratory medications for 2 days per week for 3 consecutive weeks out of a 4 week diary period is being used to define CRM), eye examination data, parental respiratory questionnaire (illnesses, medications, medical visits, ER visits, hospital admissions for CRM), and safety laboratories. Visit 15-19 (7 months CGA – 11 months CGA) will be telephone visits. Period 2 will end with Visit 20 (12 months CGA \pm 2 weeks) and will include Visit 6 parameters, review of 28-day diaries, hearing screen, parental respiratory questionnaire, and CC10-related study laboratories (see Table 3). Period 3 follow-ups, beyond 12 months CGA, will include Visit 21 (18 months CGA \pm 2 weeks) which includes Visit 6 parameters, 28-day diaries, parental respiratory questionnaire, and Bayley III Infant Neurodevelopmental Exam. Protocols for standardization of all clinical procedures will be included in the study Manual of Operations (MOO). One month before visit 21 (18 month CGA), study coordinators will send the diaries to the parents/guardians and follow-up with a call to verify that these will be completed and brought in for visit 21 (18 month CGA \pm 2 weeks).

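### The 82% power is presented for death or CRM, the 12-month primary endpoint, but its input rates are death or respiratory re-admission at 6 months, so power for the primary endpoint is undetermined

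*Combined protocol and SAP*

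**What the plan says.** **The claim.** The Power Analysis paragraph of section 8.5 states that the trial is "powered for the comparison of the two doses combined versus placebo for the composite endpoint of death or development of CRM". Section 8.1 fixes the time point: the primary outcome is "survival without CRM through 12 months CGA".

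**What counts as CRM.** Section 8.1 uses a diary score of wheeze or cough and questionnaires covering "decrease in respiratory illness requiring medications, unscheduled medical visits and/or ER or hospital admissions". Section 6.4 adds medication to the diary rule for CRM, beside persistent cough and wheeze: "use of respiratory medications for 2 days per week for 3 consecutive weeks out of a 4 week diary period is being used to define" the condition.

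**Where the rates come from.** The same Power Analysis paragraph turns to a narrower outcome: "It is important to address the combined endpoint of death or re-admission to the hospital for respiratory problems". Its data are from the pilot: "At 6 months, 3 of the 6 infants on placebo with follow-up were re-admitted to the hospital for respiratory problems", against none of 11 on rhCC10. One infant in each of the three pilot groups was lost and one in each rhCC10 group died. All three lost infants are assumed to have died or had respiratory disease, which gives 0.57 and 0.27. The 82% is conditional on similar proportions in the new trial, with 44 against 44 and alpha 0.05.

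**How the trial will be analysed.** The Efficacy evaluation paragraph of section 8.5 plans a 2 x 2 chi-square test on the binary endpoint, and "the last observation carried forward (LOCF) imputation method will be applied for early dropouts".

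**The concern.** The endpoint named for the power and the endpoint that supplied the rates differ in three ways.

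- **Content.** Hospital admission is one component of CRM. Diary symptoms, respiratory medication and unscheduled visits also count, and none of them enters 0.57 or 0.27.
- **Time.** The rates are for 6 months; the primary endpoint runs through 12 months CGA.
- **Losses.** The rates count every lost infant as a failure. The planned analysis carries the last observation forward.

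The condition that proportions be similar therefore asks 6-month death-or-re-admission rates to stand in for 12-month death-or-CRM rates, and the plan offers no reason why they should.

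What is at stake is how the result will be read. Section 8 says the findings will guide the choice of outcome variables and the size of a later trial. A null 12-month result labelled as 82% powered would look like evidence against an effect, although no power was ever derived for that endpoint.

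**Working it through.** **1. Rebuild the rates** (sections 2.5.1 and 8.5).

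- Placebo: (3 re-admitted + 1 lost) / 7 = 4/7 = 0.571.
- rhCC10: (0 re-admitted + 2 deaths + 2 lost) / 15 = 4/15 = 0.267.

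These match the stated 0.57 and 0.27. No diary, medication, unscheduled-visit or 12-month datum is used.

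**2. Reproduce the 82%.** For n = 44 per arm and a two-sided 0.05 chi-square test without continuity correction, with p̄ = (p1 + p2)/2:

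power = Φ{ [ |p1 − p2| − 1.96 √(2p̄(1 − p̄)/n) ] / √[ (p1(1 − p1) + p2(1 − p2))/n ] }

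With p1 = 0.57, p2 = 0.27 and p̄ = 0.42, this is (0.30 − 1.96 × 0.1052) / 0.1002 = 0.935, and Φ(0.935) = 82.5%. The exact power of the chi-square test is 82.6%. The plan's figure is confirmed for those rates.

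**3. Move to a broader endpoint.** The documents give no 12-month rates, so what follows is assumption. Let q be the share of placebo infants free of death and re-admission who nevertheless have other CRM. The placebo rate becomes 0.57 + 0.43q.

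- Case A: rhCC10 does not affect those other events, so its rate is 0.27 + 0.73q.
- Case B: rhCC10 reduces them by the pilot-based relative risk, 0.27/0.57 = 0.474, so its rate is 0.27 + 0.73 × 0.474q.

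| q | Placebo | rhCC10, case A | Power A | rhCC10, case B | Power B |
|---|---|---|---|---|---|
| 0.1 | 0.613 | 0.343 | 72% | 0.305 | 84% |
| 0.2 | 0.656 | 0.416 | 62% | 0.339 | 86% |
| 0.3 | 0.699 | 0.489 | 52% | 0.374 | 88% |
| 0.4 | 0.742 | 0.562 | 42% | 0.408 | 90% |

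**4. Hold the odds ratio instead.** (0.27/0.73) / (0.57/0.43) = 0.28. For placebo rates of 0.6, 0.7 and 0.8, the rhCC10 rates are 0.295, 0.394 and 0.527, and power is 83%, 83% and 78%.

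**5. Change only the coding of losses.** With lost infants as non-events and both deaths kept, the pilot gives 3/7 against 2/15, and power is 88%.

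**6. Detectable difference.** Solving the formula in step 2 for 80% power gives 0.283, 0.293, 0.293 and 0.279 at placebo rates of 0.5, 0.6, 0.7 and 0.8.

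**The case against.** The plan hides nothing. Section 8.5 names the pilot, the re-admission outcome, the 6-month time point and the treatment of losses, and makes the power conditional. Re-admission is also not foreign to the endpoint: section 2.5.1 reports it among measures of CRM, and section 8.1 includes hospital admissions in the questionnaire. Section 8 calls the endpoints exploratory. All of this stands and limits the weight of the point. It does not make 82% the power for 12-month death or CRM, because the carry-over is neither stated as an assumption nor justified.

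Four stronger readings are tempting, and the documents do not support them.

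- **That the calculation is wrong.** It reproduces.
- **That the trial is underpowered.** Dilution (case A) requires rhCC10 to have no effect on any CRM event short of re-admission. Section 2.3 argues for an effect on CRM generally, and case B raises the power.
- **That the coding of losses inflates the figure.** Counting losses as failures lowers it, 82% against 88%, so the plan's description of that choice as conservative is fair. The remaining issue is inconsistency with LOCF.
- **That only respiratory deaths count as failures in the analysis.** Section 8.5 says such deaths are failures. It does not say that other deaths are not, and both survival without CRM in section 8.1 and the composite in the Power Analysis paragraph can be read to include every death.

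**Conclusion.** The point holds as a mismatch between the endpoint and its inputs. The 82% is the power to detect 0.57 against 0.27, rates observed or assumed for death or respiratory re-admission at 6 months. Power for 12-month death or CRM is undetermined. Under the stated assumptions it runs from 42% (case A, q = 0.4) to 90% (case B, q = 0.4), and stays at 78% to 83% if the odds ratio of 0.28 carries over to placebo rates of 0.6 to 0.8. The direction of any error is not established. The ranges rest on 44 infants per arm, a two-sided 0.05 chi-square test without continuity correction, and values of q that the documents do not supply.

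**What to change.** In the Power Analysis paragraph of section 8.5:

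1. Restate the figure as 82% power to detect 0.57 against 0.27, rates taken from 6-month death or respiratory re-admission in the pilot with losses counted as failures.
2. Remove the statement that this is the power for death or development of CRM at 12 months.
3. Add either a table of power over assumed 12-month death-or-CRM rates, covering values both less and more favourable than 82%, or the detectable difference at 80% power (about 0.28 to 0.29 for placebo rates of 0.5 to 0.8). Say that losses are coded as failures in the pilot rates but handled by LOCF in the analysis.

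The cost is wording and one short table. It needs no new data, more infants, or change to the test or alpha. A single figure gives way to a range.
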